#### **7.1.2. Dose number**

- The study dose number is defined in reference to the number of study visits at which vaccination occurred. More specifically dose 1 refers to all vaccines administered at the first vaccination visit while dose 2 corresponds to all vaccinations administered at the second vaccination visit even if this is the first time a product is administered to the subject.
- Relative dose: the relative dose for an event (AE, medication, vaccination) is the most recent study dose given before an event. In case the event takes place on the day a study dose is given, the relative dose will be that of the study dose, even if the event actually took place before vaccination. For instance, if an adverse event begins on the day of the study vaccination but prior to administration of the vaccine, it will be assigned to this dose. In case a study dose is not administered, and an event occurs after the subsequent study dose (e.g., 2nd study dose), the relative dose of the event will be study dose associated to the subsequent study dose (e.g., dose 2).
- The number of doses for a product is the number of times the product was administered to a subject.
- The incidence per dose is the number of vaccination visits at which an event was reported among all vaccination visits.

## 7.2. Demography

For a given subject and a given demographic variable, missing measurement will *not be replaced* except for age.

Age will be calculated as the number of years between the date of birth and the date of first vaccination.

To ensure that the collection of date of birth will not jeopardise the privacy of Personally Identifiable Information (PII), only a partial date of birth (MMYYYY) will be collected. Therefore, the 15th of the month will be used to replace the missing date.

In case the month is missing, the date will be replaced by the June 30th of the year.

Note that due to incomplete date, the derived age may be incorrect by 1 month when day is missing from the birthdate. This may lead to apparent inconsistency between the derived age and the eligibility criteria/the age category used at enrolment.

*Also note that due to some countries' restrictions regarding collecting the full date of birth at the start of ZOSTER-049 study, in some subjects the date of birth information collected in ZOSTER-049 study was less complete than the date of birth collected in ZOSTER-006/022 (e.g., only the year of birth was collected for ZOSTER-049 study). Consequently, the calculation of age would be different for some subjects when using the date of birth info collected in ZOSTER-049 vs. in ZOSTER-006/022. To be consistent with the analyses already done in previous ZOSTER-006/022 studies, the calculated age as on 1st vaccination from ZOSTER-006/022 study will be used. For calculation of age as on enrolment day/additional dose in ZOSTER-049 study, the age difference between the first vaccination in ZOSTER-006/022 and enrolment day/additional dose should be calculated and added to the age calculated as on the 1st vaccination in ZOSTER-006/022 studies.*

Interval (in years) between the end of study efficacy cut-off date (21 April 2015) of ZOSTER-006/022 and the first and last visit of the LTFU and control group will be calculated by dividing the number of months between the two dates by 12. The same method is used to calculate the interval (in years) between the second dose of ZOSTER-006/022 and the first dose in the revaccination group and the 1-additional group and the first visit for the control group.

## 7.3. Method for Vaccine Efficacy

### 7.3.1. Efficacy data

There is no concurrent placebo/control group in this study, therefore efficacy estimates derived from ZOSTER-049 are not equivalent to vaccine efficacy estimated in well-controlled randomized studies. Any comparison with ZOSTER-006/022 estimates should be considered with caution.

*An “event” in the efficacy analysis is defined as an endpoint of interest. This could be HZ confirmed case, PHN or HZ related complications (other than PHN). The incidence rate of an “event” is determined with reference to the first “event” observed in the subject, should several “events” occur in the same subject.*

The follow-up time already observed for each subject at inclusion in ZOSTER-049, and at the time of discharge will be calculated and accounted in the assessment of HZ rate estimates of the HZ/su vaccine group.

The follow-up time for each subject **will start:**

**If the follow-up period to be considered is the duration over ZOSTER-049 study**

- *The date of the first visit in the study ZOSTER-049 study*

**If the follow-up period to be considered is from the primary study ZOSTER-006/022 study**

- *at the day after first vaccination (Month 0) if analyses are done on the Total Vaccinated Cohort for efficacy, or*
- *at 30 days after second vaccination (Month 3) if analyses are done on the mTVC or ATP cohort for efficacy.*

The follow-up time for each subject **will end:**

- at the time of the event; or,
- *at the time of receiving any vaccination for shingles which is not assigned as per protocol (for mTVC only); or,*
- at the latest visit for which data is available for subjects in case of no event. Practically, this will be set at the minimum date between the following dates
  - Date of withdrawal
  - Date of death *collected on the conclusion page for the subject who died*
  - Date of study conclusion
  - Cut off date for interim reporting for Y2, Y4

Start date of confirmed HZ case will be the earliest of the start date of the rash or start date of the pain to assess the onset of HZ, whichever comes first.

***Consideration on subjects who had HZ/PHN/HZ related complication (other than PHN) cases in ZOSTER-006/022 studies and were enrolled into ZOSTER-049 study:***

- *For the VE analysis in the prevention of HZ/PHN/HZ related complication (other than PHN) over the total duration of the ZOSTER-049 study, these subjects with previous confirmed cases will be excluded from ZOSTER-049 data.*

- *For the VE analysis in the prevention of HZ/PHN/HZ related complication (other than PHN) from one month post dose 2 in the ZOSTER-006/022 studies until the end of the ZOSTER-049 study, the first confirmed case will be considered, and the corresponding follow-up times will be censored to the time at 1st confirmed episode.*

*As there is no elimination code in primary studies ZOSTER-006/022 which eliminate subject with confirmed HZ episode, it will not be identified by elimination but rather by creating flag based on the w\_algo dataset generated during primary analysis.* The follow-up time will be calculated in days as Date of end of follow-up period – Date of vaccination +1 and expressed in person-years at risk (number of days/365.25).

For the clinical endpoint linked to a **confirmation of HZ**, since there is no possibility to confirm a suspected HZ case during the gap, the follow-up time for subjects who came back to ZOSTER-049 will be computed minus the gap between the end of study efficacy cut-off date (21 April 2015) of ZOSTER-006/022 and the first visit for each subject **in ZOSTER-049**.

### 7.3.2. Sensitivity analysis Bayesian method

Bayesian method may be used to reflect the sample distribution of the HZ cases in the control group, should a placebo arm be available in ZOSTER-049. The method will provide posterior predictive credible interval around the expected HZ incidence rate for the placebo historical controls and will be used to provide uncertainty estimates around the vaccine efficacy. The Poisson-regression model and other details of the methodology will be identical to the method described above. Non-informative (Jeffrey's) prior will be used in order to provide means and variance estimates very close to the frequentist estimates.

### 7.3.3. Method for determining Historical Control Reference Group for Planned Analysis

The proposed model is specified prior to performing any interim analysis and is based on analysis performed on previous studies ZOSTER-006/022.

*Since there is no concurrent placebo group in ZOSTER-049, incidence rates estimations on the hypothetical Control group in ZOSTER-049 study are done by utilizing Poisson regression model using data from the Placebo group in ZOSTER-006/022 study to obtain the coefficients for region and by age strata (based on age on primary vaccination). The resulting estimated incidence rate adjusted for region and by age strata are then multiplied by the actual follow-up (FU) time observed in the ZOSTER-049 study (all vaccinated subjects) to obtain the estimated number of HZ cases on the hypothetical Control group. The same incidence rate estimates by region and by age strata will be used in both yearly and overall VE calculation.*

The statistical methodology used to estimate the incidence rate on the hypothetical ZOSTER-049 control from the historical control reference group is described below. The calculation of the vaccine efficacy is based on the methodologies used in the Merck paper (Morrison) and will be done stepwise as described below:

1. Poisson regression models are used to estimate the incidence rate for HZ for the ZOSTER-049 study hypothetical placebo group based on historical controls from ZOSTER-006/022 study:

A Poisson regression model based on placebo's HZ rates in ZOSTER-006/022 studies is developed for estimating the regression coefficient in each age strata (age at first vaccination in ZOSTER-006/022 studies): **50-59, 60-69, 70-79, ≥80, ≥ 60, ≥ 70 YOA.**

$$\text{Ln}(r_{\text{HZplacebo in zoster-006/022}}) = \alpha + \beta_{\text{Australasia}} * \text{RegionAustralasia} + \beta_{\text{Europe}} * \text{RegionEurope} + \beta_{\text{North America}} * \text{RegionNorth America} + \beta_{\text{Latin America}} * \text{RegionLatin America}$$

Where

- $\text{Exp}(\alpha)$  = mean HZ rate across all regions
- Region\_Australasia, Region\_Europe, Region\_North America, Region\_Latin America are indicator variable(1/0)
- $\beta_{\text{Australasia}}, \beta_{\text{Europe}}, \beta_{\text{North America}}, \beta_{\text{Latin America}}$ : estimated region-specific Poisson regression coefficients for HZ rate.

***To note - North America is used as reference group***

2. Determine the Age adjusted historical control rate:

Using the coefficients from the Poisson regression in (1), the age-specific HZ incidence rates for an age stratum for Placebo group will be calculated as:

$$\text{Age specific } r_{\text{HZhistorical control reference group}} = \exp(\alpha + \beta_{\text{Australasia}} * \text{Region_Australasia} + \beta_{\text{Europe}} * \text{Region_Europe} + \beta_{\text{Latin America}} * \text{Region_Latin America})$$

Once the age-specific incidence rates are calculated for the historical control data from the ZOSTER-006 and ZOSTER-022, the results will be used to calculate age-specific controls rates on the hypothetical control group for the ZOSTER-049 interim and final analyses.

3. Determine the number of HZ cases for the age adjusted historical controls:

For each scheduled analysis, the age-specific follow-up time observed in ZOSTER-049 will be used as the follow-up time on the corresponding age-specific hypothetical control on ZOSTER-049. The total number of subject-years of HZ surveillance ( $F_{\text{Age}}$ ) for each age-strata will be then multiplied by the age-specific incidence rate that was estimated from step 2, to obtain the expected number of evaluable cases of HZ ( $n_{\text{Age}}$ ) for a specific age strata in the hypothetical control in ZOSTER-049:

$$n_{\text{Age}} = F_{\text{Age}} * \exp(\alpha + \beta_{\text{Australasia}} * \text{RegionAustralasia} + \beta_{\text{Europe}} * \text{RegionEurope} + \beta_{\text{Latin America}} * \text{RegionLatin America})$$

Once the expected number of cases for the hypothetical controls are determined for each age strata, expected HZ incidence rate for the hypothetical controls will be calculated by summing the numbers of expected evaluable cases of HZ for each age strata, and dividing by the total number of subject-years of HZ surveillance among all subjects during the ZOSTER-049 study.

*For the overall calculation of VE starting from the ZOSTER-006/022 study, the observed incidence rate for Placebo during ZOSTER-006/022 and the predicted incidence rate during ZOSTER-049 will be used in the calculation.*

*In the situation that there are very few subjects during the last year of follow-up with limited total follow-up time, data from both year 11 and year 12 will be pooled in the VE analysis.*

*For the sensitivity analysis considering subjects aging when enrolled into ZOSTER-049 from ZOSTER-006/022. The same step 1,2 and 3 will be used to calculate the incidence rates on ZOSTER-049 historical control using data from ZOSTER-006/022 control. The only difference is that estimated incidence rates will be applied to the age-specific group based on the approximate age in years when the subjects were enrolled in the beginning of study ZOSTER-049 to estimate the HZ cases in the hypothetical control.*

*For the VE analysis for PHN or HZ related complication (other than PHN) the same poison regression models detailed in step 1, 2 and 3 will be used to generate the hypothetical controls for the incidence of PHN or HZ related complication (other than PHN) in study ZOSTER-049.*

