**CONFIDENTIAL**

201190 (ZOSTER-049 EXT:006-022)  
Protocol Amendment 5 Final

The primary analysis will be to assess the VE during this study and will use the historical control estimates adjusted for age at randomisation during the ZOSTER-006/022 studies. The method using the historical control estimates will be further explained in the Statistical Analysis Plan (SAP). Vaccine effects will be estimated by calculating the VE and estimating 95% CIs based on the variance of the observed population in this study and treating the historical control as constant.

The secondary analysis will be to assess the VE over each year of follow-up. Results from the ZOSTER-006/022 studies will be pooled for each year after vaccination with methods used in these studies. For overlapping years between ZOSTER-006/022 studies and this study, all the data will be pooled. For the non-overlapping years only the data from this ZOSTER-049 study will be used.

The assessment of the VE over the overall period including period from vaccination during the ZOSTER-006/022 studies up to the end of this long-term study will be done with a method that will be described in the SAP.

Any available information for the diagnosis of HZ episodes (clinical diagnosis, PCR, laboratory methods, etc.) during the interval between the end of the ZOSTER-006/022 studies and beginning of the ZOSTER-049 study is to be collected. Confirmation of all of these cases in the exact way as what will be done for cases collected during the clinical study follow-up periods of the ZOSTER-006, ZOSTER-022 and ZOSTER-049 will not be possible. Therefore, these cases will not be part of all efficacy analyses. A sensitivity analysis to assess the impact of these cases on the VE will be performed (this will be described in the SAP).

The purpose of these analyses will be descriptive and therefore the CIs will not be adjusted for multiple testing.

The analyses will be performed for confirmed HZ cases, for PHN and for complications (other than PHN).

Any exploratory or sensitivity analysis may be performed in addition to the analyses described above on an ad-hoc basis. However, the significance level of those analyses may not be fully controlled.

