The primary analysis (A) will assess the VE during this study and will use the historical control estimates adjusted for region and age categories at randomization/vaccination during the ZOSTER-006/022 studies. Vaccine effects will be estimated by calculating the VE and estimating 95% CIs based on the variance of the observed population in this study and treating the historical control as constant, similarly, as described in [Morrison, 2015]. The secondary analysis C in [Table 1](#) will assess the VE over each year of follow-up, similarly to what is planned in analysis A.

See Section [7.3](#) for more details on the vaccine efficacy methodology.

The purpose of these analyses will be descriptive and therefore the CIs will not be adjusted for multiple testing.

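### SAP 7.3.3 steps 1 to 3 misstate the region-by-age calculation behind the expected control cases: pooled person-years meet a region-dependent rate, and the intercept is mislabelled

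*SAP*

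**What the plan says.** SAP 6.2.1 bases the primary analysis on "historical control estimates adjusted for region and age categories at randomization/vaccination during the ZOSTER-006/022 studies". Protocol 11.7.2 promises adjustment for age only and leaves the method to the SAP, so the region adjustment comes from the SAP.

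SAP 7.3.3 builds the control in three steps:

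- **Step 1** fits a Poisson model to the ZOSTER-006/022 placebo data within each age stratum. The equation has an intercept α and a coefficient for each of four regions, with 0/1 region indicators. It defines exp(α) as the "mean HZ rate across all regions". A note then adds that "North America is used as reference group".
- **Step 2** writes the stratum's rate as the exponential of α plus the Australasia, Europe and Latin America terms.
- **Step 3** says "the age-specific follow-up time observed in ZOSTER-049 will be used as the follow-up time on the corresponding age-specific hypothetical control". The stratum total, F_Age, "will be then multiplied by the age-specific incidence rate that was estimated from step 2, to obtain the expected number of evaluable cases of HZ". The only summation stated is over age strata.

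Three other places bear on the intent. The opening narrative of 7.3.3 describes the rate estimates as being by region and by age stratum. Section 7.3.4 puts region in the VE model as a fixed effect. Section 6.2.2.4 plans VE by region.

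**The concern.** The region indicators take a definite value only for one region at a time. F_Age is a total over all regions. Multiplying the two without splitting F_Age or summing over regions leaves n_Age undefined for any stratum with subjects in more than one region. A programmer has to supply the missing step, and the false definition of exp(α) points to a wrong one: if exp(α) really were the all-region mean, applying it to the pooled person-years would look reasonable.

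The expected count is the comparator for the primary VE. It also serves the age-specific and yearly estimates from ZOSTER-049, the PHN and complication analyses (which reuse the same steps), and the ZOSTER-049 part of the combined analysis B. Section 6.2.1 treats the historical control as a constant, so an error in the count would not show in the confidence interval. Protocol 11.4 expects 50% to 55% of subjects not to return, so the regional mix of the placebo data cannot simply be assumed to carry over.

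**Working it through.** The documents give no regional placebo rate, no regional share of follow-up and no expected case count, so there is no stated figure to reproduce. The check is of the algebra, followed by an illustration on assumed rates.

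**1. Step 1 as printed.** The four region indicators add to 1 for every subject, which is the intercept column. The equation therefore has 5 parameters and a design matrix of rank 4, and needs a constraint. The note supplies one: North America is the reference, so its coefficient is 0.

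**2. What exp(α) is.** For a North America subject all remaining indicators are 0, so the modelled rate is exp(α). It is the North America rate in that stratum. It equals an all-region mean only in special cases, such as equal regional rates.

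**3. What step 3 needs.** Evaluated at 1/0 for each region in turn, the step 2 expression yields four rates per stratum. The count that respects region is

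n_Age = Σ over regions of F_(Age,region) × exp(α_Age + β_(Age,region)), with β = 0 for North America.

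The same coefficients serve. Only the region index and the sum are missing.

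**4. Illustration.** Assumptions:

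- One stratum of 10,000 person-years.
- North America rate 10 per 1000 person-years. The figure is quoted in Protocol 1.1 for people aged 60 and over; assigning it to North America is an assumption.
- Follow-up shares w: North America 20%, Australasia 20%, Europe 50%, Latin America 10%.
- Rate ratios RR to North America as in the table.
- VE of 80%, a value used in the protocol's own power tables, and VE = 1 − observed/expected. Observed cases are held fixed so that the region-by-age sum gives the true VE.

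Let M = Σ w × RR. The region-by-age sum gives 100 × M expected cases; F_Age × exp(α) gives 100. The reported VE under the second reading is 1 − (1 − true VE) × M.

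| RR: N. America / Australasia / Europe / Latin America | M | Expected, region-by-age | Expected, exp(α) | Reported VE (true 80%) |
|---|---|---|---|---|
| 1 / 1 / 1 / 1 | 1.00 | 100 | 100 | 80.0% |
| 1 / 1.5 / 0.8 / 0.7 | 0.20 + 0.30 + 0.40 + 0.07 = 0.97 | 97 | 100 | 1 − 0.2 × 0.97 = 80.6% |
| 1 / 0.7 / 0.8 / 0.6 | 0.20 + 0.14 + 0.40 + 0.06 = 0.80 | 80 | 100 | 1 − 0.2 × 0.80 = 84.0% |
| 1 / 1.4 / 1.2 / 1.1 | 0.20 + 0.28 + 0.60 + 0.11 = 1.19 | 119 | 100 | 1 − 0.2 × 1.19 = 76.2% |

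At a true VE of 65% the last two rows give 1 − 0.35 × 0.80 = 72.0% and 1 − 0.35 × 1.19 = 58.4%.

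A second assumed set has rates of 8, 9, 7 and 10.5 per 1000 for North America, Europe, Latin America and Australasia, with shares 15/55/10/20%. The weighted mean is 1.20 + 4.95 + 0.70 + 2.10 = 8.95. With exp(α) = 8, the reported VE is 1 − 0.2 × 8.95/8 = 77.6%.

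**5. Other ways of filling the gap**, using the second table row (M = 0.97, so 19.4 observed cases). Putting person-year shares in place of the indicators gives 93.6 expected cases and VE 1 − 19.4/93.6 = 79.3%. Using one region's rate for the whole stratum gives 70 to 150 expected cases and VE from 72.3% to 87.1%. Both depart further from the text than the exp(α) reading: the first needs fractional indicators, and the second picks a region arbitrarily.

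**The case against.** The strongest reply is that the SAP, read as a whole, already describes the right calculation. The narrative of 7.3.3 speaks of rates by region and by age stratum. Region as a fixed effect in 7.3.4 needs control cases and person-years by region, and VE by region in 6.2.2.4 needs region-specific expected counts. A single pooled n_Age could supply neither. With indicators at 1/0 per region and follow-up split accordingly, the printed coefficients give the region-standardised count. All analyses are descriptive with no success criteria, and every VE shift above prices a misreading on invented rates.

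Most of this stands. A reader might infer that the promised region adjustment is not delivered, or that no reading of the formula delivers it. The documents do not support that: the intended calculation is recoverable and would deliver it. A reader might also count the missing North America term in steps 2 and 3 as an error. It is not, because under reference coding that coefficient is zero. The surplus term is the one in step 1.

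What remains is that the operative text contradicts the intent. The worked table in 7.3.6, for an analysis said to reuse the same three steps, has one rate and one follow-up time per age group and no region dimension. Its overall version multiplies the estimated rate by total follow-up. Section 7.3.4 refers the reader to 7.3.2, the Bayesian section, for steps that are in 7.3.3.

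**Conclusion.** The point holds as an error in a stated formula and a stated definition. Step 3 gives no valid single value for a stratum spanning regions, and exp(α) is the North America rate, contrary to its label. Two competent programmers could obtain different primary results from this text.

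Using exp(α) as the rate for a pooled stratum would bias the expected count whenever the person-time-weighted regional rate differs from the North America rate. Under the assumed rates a true VE of 80% becomes about 76% to 84%: too high if North America is a high-rate region, too low if it is a low-rate one. These figures rest on assumed regional rates and shares and on a simple observed-to-expected ratio in place of the planned Poisson model. It would be tempting to conclude that the primary VE is biased by some such amount. The documents do not show this, and there is no effect if regional rates are equal or if the program already works by region-by-age cell.

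**What to change.** - **Step 3:** replace the formula by n_Age = Σ over regions of F_(Age,region) × exp(α_Age + β_(Age,region)), with β = 0 for North America. This equals summing, over subjects, each subject's person-years times the predicted rate for that subject's stratum and region. Keep the region-level counts, since 7.3.4 and 6.2.2.4 need them.
- **Step 1:** delete the North America term and define exp(α_Age) as the North America rate in that age stratum.
- **Section 7.3.6:** use the same region indexing in the table and in the overall version.
- **Section 7.3.4:** change the cross-reference from 7.3.2 to 7.3.3.

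The cost is a text correction and a check that the analysis program sums region-by-age cells. No new data are required. If the program already does so, no result changes.

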### 11.7.2. Analysis of efficacy (LTFU and Control groups)

The primary analysis of efficacy will be performed on the mTVC, the analysis will be also performed on the TVC and the ATP for efficacy to complement the mTVC analysis.

The analysis on mTVC and ATP cohort for efficacy will be performed over the follow-up time from one month post Dose 2 to the confirmed HZ case for a subject with a confirmed HZ case, and to the date of last contact for subjects without a confirmed HZ case.

The analysis on the TVC will be performed over the complete follow-up period and will include confirmed HZ cases from Dose 1 for vaccine efficacy evaluation. The end of the follow-up period will be calculated according to the same principle as will be done for the mTVC and ATP analyses for efficacy, i.e., up to the confirmed HZ case for a subject with a confirmed HZ case, or up to the date of last contact for subjects without a confirmed HZ case.

All analyses will be performed overall and by age strata. The age strata for reporting purposes are 50-59, 60-69, and,  $\geq 70$  YOA at primary vaccination. When overall VE is presented, the age factor will include the 3 main age strata 50-59, 60-69, and  $\geq 70$  YOA. When VE by age is presented, the same model will be run using only the data pertaining to the strata under consideration.

In addition, the analysis will be performed on subjects  $\geq 60$  YOA at inclusion in the ZOSTER-006/022 studies.

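### The ≥60 and ≥70 hypothetical-control rates in SAP 7.3.3 carry no age term, and step 3 does not name the disjoint age strata to be summed

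*SAP*

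**What the plan says.** SAP 7.3.3 step 1: a Poisson model on placebo HZ rates "is developed for estimating the regression coefficient in each age strata". The strata listed are "50-59, 60-69, 70-79, ≥80, ≥ 60, ≥ 70 YOA". The covariates are region terms only.

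Step 3: follow-up time "for each age-strata will be then multiplied by the age-specific incidence rate that was estimated from step 2". The overall control rate comes from "summing the numbers of expected evaluable cases of HZ for each age strata" and then "dividing by the total number of subject-years of HZ surveillance among all subjects during the ZOSTER-049 study". No subset of the six strata is named for the sum.

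The same section applies one set of region-by-age rates to both yearly and overall VE, and uses the same steps for PHN and other complications.

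SAP 6.2.1 says the primary analysis uses "historical control estimates adjusted for region and age categories at randomization/vaccination".

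Protocol 11.7.2: "When overall VE is presented, the age factor will include the 3 main age strata 50-59, 60-69" and ≥70. For VE by age, "the same model will be run using only the data pertaining to the strata under consideration". It leaves the historical-control method to the SAP.

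SAP 7.3.4 names region as a fixed effect in the VE model, run in the six strata and overall. It names no age factor.

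**The concern.** A ≥70 model with region terms alone returns the average placebo rate in each region, weighted by the placebo group's own ages. If the people followed in ZOSTER-049 have a different share aged ≥80, that average is the wrong comparator for them. The same holds for ≥60 and the split between 60-69 and ≥70. It also means that n(≥70) from its own model need not equal n(70-79) + n(≥80), so two VE estimates in one table can rest on inconsistent controls. A pooled rate also cannot follow a change in age mix from one follow-up year to the next.

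The gap in step 3 is separate. The documents offer two disjoint partitions: three strata in protocol 11.7.2, and four 10-year strata within the SAP list. Step 3 chooses neither. With no concurrent control, the expected count is the comparator for every VE estimate, so a second statistician should be able to reproduce it from the SAP alone.

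**Working it through.** **The plan's own figure.** Protocol 11.4 gives 7344 × 0.50 = 3672 from ZOSTER-006 and 6075 × 0.45 = 2733.75 from ZOSTER-022. The total is 6405.75, which reproduces the stated 6406. The documents give no expected control count, so what follows is illustration.

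**Size of the age-mix effect.** If the control is too high by a factor k, a true VE reads as 1 − (1 − VE)/k.

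*≥60.* Let s and t be the shares of ZOSTER-006 aged 60-69 and ≥70 (not given, so varied), and ρ the ratio of the ≥70 rate to the 60-69 rate (assumed 1.0 to 1.5). ZOSTER-022 is all ≥70. Taking the vaccine-group numbers as a stand-in for placebo, the 60-69 share among those ≥60 is

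- source: w_p = 7344s / [7344(s+t) + 6075]
- returners: w_r = 3672s / [3672(s+t) + 2733.75]

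and k = [w_p + (1−w_p)ρ] / [w_r + (1−w_r)ρ].

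| s, t | w_p | w_r | excess, ρ = 1.0 | excess, ρ = 1.5 |
|---|---|---|---|---|
| 0.2, 0.2 | 0.163 | 0.175 | 0% | 0.42% |
| 0.3, 0.3 | 0.210 | 0.223 | 0% | 0.47% |
| 0.5, 0 | 0.377 | 0.402 | 0% | 0.96% |

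Planned return rates therefore give 0 to about 1%. As a stress case, moving the 60-69 share from 20% to 30% at ρ = 1.5 gives k = 1.40/1.35 = 1.037, and VE 80.0% reads 80.7%.

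*≥70.* All inputs are assumed: 8-9 per 1000 at 70-79, 11-12 per 1000 at ≥80, and a ≥80 share of 20-25% in placebo against 12-15% in returners.

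| Rates per 1000 (70-79, ≥80) | ≥80 share, placebo vs returners | Control rate, placebo mix / returner mix | k | VE 65% reads |
|---|---|---|---|---|
| 9, 11 | 20% vs 15% | 9.40 / 9.30 | 1.011 | 65.4% |
| 8, 11 | 25% vs 12% | 8.75 / 8.36 | 1.047 | 66.6% |
| 8, 12 | 25% vs 12% | 9.00 / 8.48 | 1.061 | 67.0% |
| 10, 10 | any | 10 / 10 | 1.000 | 65.0% |

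The last row uses the only rate the protocol gives above age 60 (section 1.1, 10 per 1000), and the effect vanishes. If returners were older than placebo, the sign would reverse.

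**Which strata are summed.** Three places bear on step 3:

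- Its denominator counts each subject-year once, which fits only a numerator over non-overlapping strata.
- Protocol 11.7.2 uses three non-overlapping strata for overall VE.
- SAP 7.3.6 allocates expected cases n1 to n7 once each to 50-59, 60-69, 70-79 and ≥80. Its overall count, however, is a single estimated rate times total follow-up, so it does not settle the rule for step 3.

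**The case against.** Fitting within the stratum under consideration is the protocol's stated approach, so a ≥70 model on ≥70 data follows the plan. The ≥60 and ≥70 estimates are secondary and descriptive, with no success criteria. The effect is small, and the ≥70 range rests on rates and age shares found in neither document. All of this stands. It limits the size of the point, but it does not reconcile region-only models with a control described as adjusted for age categories.

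The n_Age formula carries region indicators but no region index on follow-up time. Because 7.3.3 says that rates by region and age are used, this is notation, worth tidying only because the same sentence is being edited.

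A reader might infer something stronger from step 3: that all six strata are added, so that ages 60-69 count twice and ≥70 three times, and the primary VE is inflated. With 36,000 person-years (6000 subjects for 6 years), the protocol's 5 and 10 per 1000, and ZOSTER-006 split in equal thirds, that sum would be 839 cases against 326, or 23.3 against 9.0 per 1000. The documents do not support this reading. The single-count denominator, protocol 11.7.2 and the allocation in SAP 7.3.6 all point to a disjoint sum, and a rate above 20 per 1000 beside the protocol's 10 per 1000 would be hard to miss.

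**Conclusion.** As written, the ≥60 and ≥70 controls are adjusted for region but not for age within the stratum, and nothing ties them to their component strata. The partition for the overall sum is implied but not stated. No error in the primary VE is shown. If the four 10-year strata are summed, the pooled ≥60 and ≥70 rates do not enter the primary count; if the protocol's three are summed, the pooled ≥70 rate does, which is one more reason to name the set.

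For HZ, the excess in the control is about 0-1% for ≥60 at planned return rates, and about 1-6% for ≥70 under the assumed inputs. It is zero with flat incidence from age 60. The true placebo rates by stratum, the ZOSTER-006 age split and the returners' age mix are not in the documents. The size for PHN and other complications was not estimated. The change is worth making because it costs almost nothing and removes an inconsistency, not because a large bias is likely.

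**What to change.** In SAP 7.3.3, name one disjoint partition: 50-59, 60-69, 70-79 and ≥80. Fit the placebo models in those four strata only, and write step 3 as

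n_Age = Σ over regions of F_Age,region × exp(α_Age + β_Age,region).

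Obtain the ≥60, ≥70 and overall expected counts by adding these cells, and say that the same rule applies to the yearly, PHN and complications analyses. State that this partition replaces the three strata of protocol 11.7.2 for the control count, and say in 7.3.4 whether the overall model carries an age factor. The cost is SAP wording and some reprogramming. There are fewer models to fit and no new data to collect.
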